## ABBREVIATION

Abbreviation or Acronym	Definition
AE	adverse event
ALT	alanine aminotransferase
ANCA	Anti-Neutrophil Cytoplasmic Antibodies
AST	aspartate aminotransferase
ATC	Anatomical Therapeutic Chemical
BMI	body mass index
BOR	best overall response
Bpm	beats per minute (heart rate)
CFR	Code of Federal Regulations
CNS	central nervous system
CpG	cytosine linked to a guanine by a phosphate bond
CR	complete response
CRA	Clinical Research Associate
CRO	Contract Research Organization
CT	computerized tomography
CTCAE	Common Terminology Criteria for Adverse Events
CTL	cytotoxic T lymphocyte
CTLA-4	cytotoxic T-lymphocyte-associated protein 4
CVA	cerebrovascular accident
D	day
DLN	draining lymph node
DLT	dose-limiting toxicity
DOR	duration of response
ECG	electrocardiogram
ECOG	Eastern Cooperative Oncology Group
eCRF	electronic case report form
EOT	end of treatment
FDA	Food and Drug Administration
GCP	Good Clinical Practice
HBV	hepatitis B virus
HCV	hepatitis C virus
HIV	human immunodeficiency virus
IB	Investigator's Brochure
ICF	Informed Consent Form
ICH	International Conference on Harmonization
ID	identification
IFN	interferon
INR	international normalized ratio
IRB	Institutional Review Board
irRC	Immune-Related Response Criteria
IV	intravenous
MI	myocardial infarction
MedDRA	Medical Dictionary for Regulatory Activities

Abbreviation or Acronym	Definition
MRI	magnetic resonance imaging
MTD	maximum tolerated dose
N or n	number
OBD	optimal biologic dose
ODN	oligodeoxynucleotide
ORR	objective response rate
PD	progressive disease
PD-1	programmed cell death protein 1
pDC	plasmacytoid dendritic cells
PFS	progression-free survival
PR	partial response
PTT	partial thromboplastin time
QTc	QT corrected for heart rate
QTcF	QT corrected according to Fridericia
RBC	red blood cell
RECIST	Response Evaluation Criteria in Solid Tumors
RP2D	recommended Phase 2 dose
SAE	serious adverse event
SAP	statistical analysis plan
SD	Stable disease
SOC	System Organ Class
SOP	standard operating procedure
SUSAR	suspected unexpected serious adverse reactions
TEAE	treatment-emergent adverse event
Th1	T helper cell type 1
TME	Tumor microenvironment
TLR9	Toll-like receptor 9
Treg	Regulatory T cell
TSH	thyroid stimulating hormone
TTR	time to response
ULN	upper limit of normal
U.S.	United States
WBC	white blood cell
WHO	World Health Organization
WHO-DD	World Health Organization Drug Dictionary

## 1.0 TRIAL SUMMARY

Abbreviated Title	Pembrolizumab and in-situ injection of CMP-001 for Relapsed and Refractory Lymphomas
Trial Phase	Phase I/II
Clinical Indication	Relapsed and Refractory Lymphomas
Trial Type	Single arm
Type of control	No control arm
Route of administration	Pembrolizumab intravenous injection and CMP-001 in-situ injection
Trial Blinding	No blinding
Treatment Groups	Adaptive dose-finding based on efficacy and toxicity
Number of trial participants	Maximum of 21 evaluable patients
Estimated enrollment period	3-4 years
Duration of Participation	Patient responding to treatment will be followed for 2 years. Patient progressing on treatment will come off study.
Estimated average length of treatment per patient	6 months

## 2.0 TRIAL DESIGN

### 2.1 Investigational Plan

#### 2.1.1 Overall Study Design

This is a single center, open-label, combined Phase I/II clinical study of intratumoral administration of CMP-001 and intravenous administration of pembrolizumab in selected subjects with lymphoma. The key study objective is to find a CMP-001 dose (**vidutolimod**) that in combination with pembrolizumab has optimal clinical efficacy and acceptable toxicity. Dose-finding will be performed with an adaptive clinical trial design. Secondary study objectives include characterization of safety, pharmacodynamics, and assessment of anti-lymphoma activity.

Each treatment cycle is 3 weeks in duration. The first CMP-001 injection stimulates antibody formation to the VLP of CMP-001 and will be given subcutaneously. Subsequently, CMP-001 will be administered by intratumoral injection every week for seven doses. The seventh dose, which is to be administered on Week 7 Day 1 (W7D1), represents the start of dosing at 3-week intervals (ie, with subsequent CMP-001 doses to be administered on Week 10 Day 1 [W10D1] and Week 13 Day 1 [W13D1]). Subjects enrolled into this study will continue study treatment so long as they do not experience unacceptable toxicities and in the Investigator's

opinion continued treatment is in the subject's best interest. Patient will be evaluated for treatment efficacy and toxicity up to 30 days after end of treatment and followed for long term survival for 2 years.

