- n. The 30-Day Follow-up (+7 Days) or before new treatment is started is a safety follow up visit that may be conducted in the study clinic OR via phone. The subject should be questioned for any new AEs or ConMeds, no other safety assessments are required unless the Investigator identifies a new safety concern that requires further follow-up. This visit should occur 30 days (+7) after the EOT visit. SAEs that occur within 90 days of the end of treatment or before initiation of a new anti-cancer treatment, whichever comes first should also be followed and recorded.
- o. All subjects will be followed for survival for 2 years ( $3 \pm 1$  month). Survival follow up may be accomplished by visit or phone contact for two years or until subject death, subject consent is withdrawn, subject is lost to follow up or the study is completed.

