### **8.1.3 Response/Efficacy Assessments**

Disease status will be assessed by CT or PET-CT scans. Calipers may be used to measure superficial cutaneous tumors. Scans will be obtained at Screening and on follow up as per Trial Flow Chart, Section 7. These can be performed up to five days prior to starting the next cycle of therapy. The assessment method used at Screening (baseline value) to determine disease status/progression (CT vs. PET-CT) should be used throughout the course of the study if possible.

Antitumor activity will be described as ORR using Cheson 2007.(Cheson et al., 2007) For detail refer to Appendix D. Other secondary endpoints that will be assessed include complete response (CR), progression-free survival (PFS), best overall response (BOR), time to response (TTR), stable disease (SD) and duration of response (DOR).

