## **8.1.6 Other Procedures**

### **8.1.6.1 Withdrawal/Discontinuation**

When a participant discontinues/withdraws prior to trial completion, all applicable activities scheduled for the final trial visit should be performed at the time of discontinuation. Any adverse events which are present at the time of discontinuation/withdrawal should be followed in accordance with the safety requirements outlined in Section 8.2 - Assessing and Recording Adverse Events. Participants who a) attain a CR or b) complete 24 months of treatment with pembrolizumab may discontinue treatment. After discontinuing treatment following assessment of CR, these participants should return to the site for a Safety Follow-up Visit (described in Section 8.1.7.4) and then proceed to the Follow-Up Period of the study (described in Section 8.1.7.5).

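### PFS and duration of response are listed endpoints, but the plan has no capture of progression once a patient stops treatment without progressing

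*Combined protocol and SAP*

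**What the plan says.** **Endpoints.** Section 8.1.3 states: "Other secondary endpoints that will be assessed include complete response (CR), progression-free survival (PFS", and the same sentence ends with "stable disease (SD) and duration of response (DOR". Both PFS and DOR need a progression date. Neither is defined anywhere, and no censoring rule is given.

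**Observation period.** Section 2.1.1 states: "Patient will be evaluated for treatment efficacy and toxicity up to 30 days after end of treatment and followed for long term survival". The survival period there is 2 years. Flow-chart footnote o states: "All subjects will be followed for survival for 2 years", by visit or phone. It names no imaging and no progression status. Footnote n makes the 30-day contact a safety contact about adverse events and concomitant medication, which may be by phone.

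**Scans.** Footnote l fixes one post-baseline scan, at W7D1 or after two cycles. Later scans have no set interval.

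**Stopping without progression.** Section 5.5 allows this for toxicity, at the patient's request, after a confirmed complete response (CR) and after 35 pembrolizumab treatments. Section 8.1.6.1 allows it on CR or after 24 months. Patients who stop in CR "then proceed to the Follow-Up Period of the study (described in Section 8.1.7.5"). The text runs from 8.1.7.4 straight to 8.2.

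**Trial Summary (Section 1.0).** "Patient responding to treatment will be followed for 2 years. Patient progressing on treatment will come off study". It does not say what responders are followed for.

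**The concern.** The patients whose later progression goes unrecorded are those who left treatment while still in control: complete responders, and responders who stopped for toxicity or by choice. The trial stays in touch with them for survival but has no planned way of learning when the lymphoma returned.

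DOR could then be followed only to about the time treatment stopped. In PFS, a later death could be counted as the event in place of an earlier progression that nobody recorded. Because the end of observation is linked to response and tolerability, censoring may be informative. Durability is what a reader will want to know about an immunotherapy combination in relapsed lymphoma, and here it would be the least well-observed result.

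**Working it through.** The plan gives no sizing or event count for PFS or DOR, so there is no figure to reproduce. The first two steps compare the text; the next two illustrate size.

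**1. What is planned after treatment ends**
- Up to 30 days: efficacy is nominally evaluated (2.1.1), but the only scheduled contact in footnote n asks about adverse events and medication.
- From 30 days to 2 years: survival contact (2.1.1, footnote o).
- Progression status, scan results or start of new therapy in that second window: not listed in either place.

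**2. Text pointing the other way**
- Section 1.0 follows responders for 2 years, purpose unstated.
- Section 5.4.2 mentions retreatment for relapse after CR.
- Section 5.5 says that patients off treatment continue to be monitored.
- Section 8.1.1.8 moves patients to survival follow-up once new anti-cancer therapy starts, which implies an earlier stage.
- Section 8.1.6.1 cites the absent 8.1.7.5.

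None of these gives a schedule or a data item. They suggest disease follow-up was intended but not written, and they conflict with 2.1.1 and footnote o.

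**3. How the loss depends on the stopping time**

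Inputs: response at Week 7, about 1.6 months (7 × 7 / 30.4); 6 months average treatment (Section 1.0); 30 days, about 1 month (2.1.1). Assumptions: exponential DOR, medians of 6, 12 and 24 months, and a 2-year clock from first dose.

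Share of progressions inside the window = 1 − 2^(−t / median), where t is the time from response to the end of the window.

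| Case | Window ends (month) | t | Median 6 | Median 12 | Median 24 |
|---|---|---|---|---|---|
| Stops at month 6 | 6 + 1 = 7 | 5.4 | 46% | 27% | 14% |
| CR at Week 7, then 8 further 3-weekly doses (24 weeks = 5.5 months) | 1.6 + 5.5 + 1 = 8.1 | 6.5 | 53% | 31% | 17% |
| 35 doses (34 × 3 weeks = 23.5 months) | 23.5 + 1 = 24.5 | 22.9 | 93% | 73% | 48% |
| Progression collected to month 24 | 24 | 22.4 | 93% | 73% | 48% |

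For example, with median 12, 1 − 2^(−5.4/12) = 0.268 and 1 − 2^(−22.4/12) = 0.726. Counting W7D1 as 42 days (1.4 months) changes the first row only to 48%, 28% and 15%.

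The second row uses the minimum in Section 5.5; Section 8.1.6.1 states no minimum, and the two should be reconciled. All rows are upper bounds, because they assume that a progression inside the window is detected although scans after W7D1 have no fixed interval.

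**4. Patients already off treatment and progression-free**

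This is a different quantity: among progressions within follow-up T after stopping, the share that fall after day 30 = 1 − F(30 days) / F(T), with F(t) = 1 − 2^(−t / median). The median is now the assumed time from stopping to progression.

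| T | Median 6 | Median 12 | Median 24 | Median 36 |
|---|---|---|---|---|
| 24 months (clock from end of treatment) | 88.5% | 92.6% | 94.4% | 94.9% |
| 18 months (clock from first dose, 6 months treated) | 87.7% | 91.4% | 93.1% | 93.6% |

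The documents do not say when the 2 years start, so both are shown. The 18-month row does not apply to patients treated for about 2 years, whose window closes at about the end of a clock that starts at first dose.

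**5. What does not depend on this**

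BOIN12 dose selection (Sections 2.1.2 and 9.2) uses DLT and efficacy rates. PFS and DOR are not in the Section 3.2 objectives or the Section 9 analyses.

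**The case against.** **Disease follow-up may be intended.** The passages in step 2 point that way, and the scan row of the flow chart carries no end date, whereas adverse-event monitoring explicitly ends 30 days after end of treatment. The diagram in Section 2.2 could not be read here. This stands to the extent that a reader who infers that disease evaluation certainly ceases, or that progression in responders is never collected, goes further than the text allows. What can be said is that no capture is planned and that the sections disagree.

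**No censoring rule exists.** A reader might infer that responders are censored at end of treatment plus 30 days, so that PFS and DOR merely measure when treatment stopped. No section says so, and Section 9.1 defers methods to a detailed SAP before database lock. That stands too. A later SAP can supply the rule, but it cannot supply progression dates that were not collected.

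**The size could be misread.** It is tempting to apply 46%, 27% and 14% to all responders. The 6-month figure is an average over all patients. Section 2.1.1 lets treatment continue while it is tolerated and in the patient's interest, so responders who progress on treatment are under evaluation, and those who complete 35 doses lose essentially nothing by month 24.

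**The stakes are limited.** This is a single arm of at most 21 evaluable patients with mainly descriptive analyses, and no decision rests on PFS or DOR. This limits the weight of the point but does not remove the mismatch between 8.1.3 and the follow-up plan.

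**Conclusion.** The point holds as a gap and an inconsistency. PFS and DOR are promised, yet progression has no planned capture in patients who stop treatment without progressing, and the sections that hint at disease follow-up do not provide it.

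The loss is greatest for early stoppers. For a responder due to stop at month 6, the share of progressions inside the window is lower by about 46, 46 and 33 percentage points (92.5 − 46.4, 72.6 − 26.8, 47.6 − 14.4) than with collection to month 24, for median DOR of 6, 12 and 24 months. It is negligible for patients who complete about 2 years of pembrolizumab. These sizes rest on the exponential model, the assumed medians and the assumed clock. How many patients would stop early without progression cannot be derived from the documents.

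The consequence is confined to descriptive durability results. Dose selection and its operating characteristics are untouched. The change is worth making mainly because it is cheap.

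**What to change.** - **Collection (2.1.1 and footnote o).** For patients who end treatment without progression, record at each follow-up contact already planned: disease status; date and method of any progression found on routine-care imaging; and start of new anti-lymphoma therapy. Continue until progression or 2 years, and state when the 2 years begin.
- **Definitions.** Define PFS and DOR as time to progression or death, censored at the last adequate disease assessment.
- **Cross-references.** Point 8.1.6.1 to this text in place of 8.1.7.5. Bring Sections 1.0, 5.4.2, 5.5 and 8.1.1.8 into line with 2.1.1 and footnote o on who is followed and for what.

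The cost is protocol wording and a few eCRF fields, with no added scans or visits. The drawback is that routine-care imaging is irregular, as are scans on treatment after W7D1, so progression dates will be approximate and should be reported as such. If the sponsor does not want this collection, dropping or limiting PFS and DOR in 8.1.3 would also remove the mismatch.

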### 2.1.2 Dose Finding Adaptive Design

[figure not shown]
The Bayesian optimal interval design (BOIN12) of Lin et al. (Lin, Zhou, Yan, Li, & Yuan, 2020). will be used to conduct dose finding for CMP-001 across the levels summarized in **Table 1b**. Pembrolizumab dose will be fixed at 200 mg IV every 3 weeks. In the design, patients will be assigned adaptively to CMP-001 dosing cohorts to find a dose with biologically optimal efficacy and toxicity.

**Table 1a: Dose Levels in the Adaptive Design**

Dose Level	Pembrolizumab Dose	CMP-001 Dose (mg)
1*	Per Product Label	7.5
2	Per Product Label	10

\* Starting dose

**Table 1b. Decision table to choose Case A, B, or C to determine the dose assignment for new patients**

**A maximum of 21 patients will be treated sequentially in up to 7 cohorts of three patients each. Treatment will start in the first cohort at a CMP-001 dose of 7.5 mg. After a cohort is evaluable for efficacy and dose-limiting toxicity (DLT), the next cohort will be treated at the admissible dose with highest mean utility.** Admissible dose levels ( $j$ ) are determined according to the following posterior probability criteria for their true rates of DLT ( $\pi_{T,j}$ ) and efficacy ( $\pi_{E,j}$ ):

$$\Pr(\pi_{T,j} > 0.3 | data) < 0.925$$

$$\Pr(\pi_{E,j} < 0.5 | data) < 0.90.$$

Desirable tradeoff between treatment benefit and risk is quantified with a utility function defined by the investigators to be  $\Pr(\pi_{E,j}) - 0.3 \Pr(\pi_{T,j})$ . If a dose is found to not meet the admissibility criteria during the trial, it will be eliminated from further enrollment. If the number of patients at the current dose reaches 12, the trial will be stopped. Specifically, dose selection in the BOIN12 design proceeds according to the following 3 steps.

1. Treat the first cohort at dose level  $j = 1$ .
2. Suppose that the current dose level is  $j$ , use decision Table 1a to choose one of the following three cases to determine the dose for treating the next cohort of patients.

**Case A:** Determine the desirability of dose levels  $j - 1$ ,  $j$ , and  $j + 1$  using the rank-based desirability scores (RDS) given in Table A of APPENDIX F, and choose the one that has the highest desirability to treat the next cohort. If the RDS of all three doses are “E,” stop the trial and no dose should be selected. In the case that dose level  $j - 1$  or  $j + 1$  does not exist, then apply the above rule to dose levels  $j$  and  $j + 1$  (or  $j$  and  $j - 1$ ).

**Case B:** Determine the desirability of dose levels  $j$  and  $j - 1$  using the RDS given in Table A of APPENDIX F, and choose the one that has the higher desirability to treat the next cohort. If the RDS of the two doses are “E,” stop the trial and no dose should be selected. If the current dose level  $j$  is the lowest dose, treat the next cohort of patients at the lowest dose unless the RDS of the lowest dose is “E,” at which point terminate the trial.

**Case C:** Determine the desirability of dose levels  $j$  and  $j - 1$  using the RDS given in Table A of APPENDIX F.

- If the current dose level  $j$  is the lowest dose, treat the new patients at the lowest dose unless the RDS of the lowest dose is “E,” at which point terminate the trial.
- If the current dose level  $j$  is not the lowest dose and the RDS of dose level  $j - 1$  is not “E,” de-escalate the dose to level  $j - 1$  to treat the next cohort of patients.
- If the current dose level  $j$  is not the lowest dose and the RDS of dose level  $j - 1$  is “E,” stay at the current dose level  $j$  to treat the next cohort of patients unless the RDS of dose level  $j$  is “E,” at which point terminate the trial.

3. Repeat step 2 until the maximum sample size of 21 is reached or if the number of patients treated on any dose reaches 12. Then, use the isotonic estimation method described in Lin et al. (Lin et al., 2020) to select the (biologically optimal) dose that is admissible and that has the highest estimated utility.

**We have treated 6 patients on the study so far. The first 3 patients were treated at the dose level of 5 mg and the next 2 patients at dose level 7.5 mg. The three patients treated at 7.5 mg CMP001 dose will be included to the maximum accrual goal of 21 with this updated protocol. (Previous version had target accrual of 39 patients). This means additional 18 patients are needed to complete the study. Patients treated at 5 mg included 2 patients with recent anti-B cell therapy (Rituximab, CAR T cells) and did not develop antiQbeta antibody important for CMP001 function. We updated the exclusion criteria to account for this observation.**

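### Section 2.1.2 summarises dose assignment as highest mean utility, but the steps that follow use Cases A/B/C and the RDS; the two rules can assign different doses and only the steps fit Section 9.2

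*Combined protocol and SAP*

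**What the plan says.** Section 2.1.2 contains two statements about the next cohort's dose.

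- **Bold paragraph under the Table 1b caption.** After a cohort is evaluable, "the next cohort will be treated at the admissible dose with highest mean utility". Admissibility uses posterior limits on the DLT rate (0.3, cutoff 0.925) and the efficacy rate (0.5, cutoff 0.90). Utility is the efficacy rate minus 0.3 times the DLT rate. No toxicity-based case restricts the choice.
- **The three steps.** They open with "Specifically, dose selection in the BOIN12 design proceeds according to the following 3 steps". A Case A, B or C is chosen. In Case A the candidate doses are compared on their Table A scores, with the instruction "choose the one that has the highest desirability to treat the next cohort". Case B excludes the higher dose. In Case C, above the lowest dose, the instruction is "de-escalate the dose to level" j − 1 whenever that level is not marked E, whatever the scores.

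Estimated utility returns in step 3, but only for the final selection.

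The table references are also swapped. The opening of Section 2.1.2 cites Table 1b for the dose levels, but Table 1a is captioned as the dose levels. Step 2 says to "use decision Table 1a to choose one of the following three cases", but the decision table is captioned Table 1b.

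**The concern.** Mean utility and the RDS are different statistics. The RDS depends on how much information a dose has, and it gives an untried dose a fixed rank of 62. An observed mean does not exist for an untried dose, and a posterior mean needs a prior that the text does not give. The bold sentence also omits the Case B and C toxicity restrictions.

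The trial is under way, so assignments are being made from this section. Anyone who follows the bold sentence runs a design other than the one whose operating characteristics are reported in Section 9.2 and Appendix F Table B.

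**Working it through.** **1. What Table A ranks.** Write n, T and E for patients, DLTs and responses at a dose. Scale utility to 0–1 with x = (E − 0.3T + 0.3n)/1.3 and take U ~ Beta(1 + x, 1 + n − x). Scaled utility at the two limits is (0.5 − 0.3 × 0.3 + 0.3)/1.3 = 0.546, and the midpoint between that and 1 is 0.773. Ranking Pr(U > 0.773) over the non-eliminated cells, with Beta(1,1) priors for elimination, reproduces Table A: all E cells and all 119 ranks match. The RDS is therefore a tail-probability rank.

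**2. A path where the rules part.** With no DLTs this does not depend on the case boundaries. Posterior mean utility under Beta(1,1) is (1 + E)/(2 + n) − 0.3(1 + T)/(2 + n).

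- *Cohort 1 at 7.5 mg, 2/3 responses.* RDS 69 against 62 for untried 10 mg; mean 0.54 against 0.35. Both rules stay.
- *Cohort 2 at 7.5 mg, 1/3 responses, so (n, T, E) = (6, 0, 3).* x = 4.8/1.3 = 3.69 and Pr(U > 0.773) = 0.14, against 1 − 0.773 = 0.23 for an untried dose. RDS 49 < 62 assigns 10 mg. Mean utility is 4/8 − 0.3 × 1/8 = 0.46, against 0.50 − 0.15 = 0.35, and assigns 7.5 mg.
- *Continue by RDS.* One response in 3 at 10 mg gives RDS 42 < 49, so the trial returns to 7.5 mg. One response in 3 there gives (9, 0, 4) against (3, 0, 1). RDS 36 < 42 assigns 10 mg. Observed mean utility 4/9 = 0.444 against 1/3 = 0.333 assigns 7.5 mg, as does the posterior mean (0.427 against 0.340). No prior for an untried dose is involved here.

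**3. How often.** In trials run by the RDS steps, the bold sentence read with posterior means would change at least one assignment in 44% of trials in Scenario 5, 48% in Scenario 6 and 5% in Scenario 1.

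**4. Operating characteristics.** All cohort outcomes were enumerated exactly: cohorts of 3, maximum 21, stop at 12 on a dose, efficacy and DLT independent. The content of Table 1b is not shown in the text available, so case boundaries of 0.236/0.359 and a minimum of 6 patients for Case B are assumptions. Ranges reflect different readings of the isotonic final selection, which the protocol does not spell out.

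| Quantity | Stated (9.2, Table B) | RDS steps | Bold sentence, posterior mean |
|---|---|---|---|
| Scenario 1, total selection | 3% | about 3% | about 3% |
| Scenario 5, total selection | 85% | 83.5–85.6% | 86.8–88.9% |
| Scenario 5, expected patients | 15.6 | about 15 | 14.3 |
| Scenario 5, 10 mg never given | not given | 14% | 25% |
| Scenario 5, 10 mg selected | 48.8% | about 50% | about 51% |
| Scenario 7, total selection | 70% | 69% (67–72%) | 74–79% |
| Scenario 9, total selection | 47% | 47% (45–51%) | 54–61% |
| Scenario 11, total selection | 24% | 25% (23–28%) | 32–37% |
| Scenario 6, patients at 10 mg | 7.2 | 6.5 | 5.5 |
| Scenario 9, patients at 10 mg | 4.4 | 4.2 | 6.1 |
| Scenario 11, patients at 10 mg | 2.7 | 2.6 | 4.9 |

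If mean utility is taken as the observed mean, 10 mg is never given in 64% of Scenario 5 trials and is selected in 25–27%, against 48.8% in Table B.

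**5. Sensitivity.** Boundaries of 0.276/0.419 leave the result unchanged and a Case B minimum of 9 leaves it similar. A minimum of 3 does not fit Table B.

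**The case against.** The strongest reply is that the protocol does state an executable rule. The steps are introduced as the specific form of the design, and they give the cases, the score table, the elimination rules and the stopping rules. Only the steps can be carried out for an untried dose without further definition. Nothing shows that the bold sentence has been used. This stands, and it limits the point: the plan has a rule, with an incorrect summary in front of it.

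A reader might infer that the bold sentence would hold the trial at 7.5 mg and leave the primary objective unanswered. The figures do not support that for the posterior-mean reading. In Scenario 5 it leaves 10 mg untried more often (25% against 14%) but selects it about as often, and total selection rises slightly. When toxicity is high it goes the other way and puts more patients at 10 mg. Larger effects in Scenario 5 (10 mg untried in 35% of trials and selected in 44%, or 71% and 22%) arise only if posterior or observed means respectively replace the RDS inside Cases A/B/C, a rule the protocol does not state.

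A reader might also infer that the RDS steps reproduce Table B exactly. They do not. Patient numbers at 10 mg are up to 0.7 low, well beyond the simulation error of 10,000 trials (about 0.06). Adding a step that is not in the text, trying 10 mg if it is still untried after 9 patients with an acceptable DLT rate, brings patient numbers within 0.13.

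Finally, Scenario 1 and, within tolerance, Scenario 5 power do not separate the rules. The totals in Scenarios 7, 9 and 11 separate the posterior-mean reading. The observed-mean reading is separated by the per-dose columns.

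**Conclusion.** The point holds as an unreconciled contradiction that should be corrected. The bold sentence and the steps are different rules, and they assign different doses on data the trial can produce. That finding rests on Table A and simple arithmetic and needs no assumption about Table 1b.

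The size of the effect does rest on the assumed boundaries, the Case B minimum and independence of efficacy and DLT. With posterior means, the literal sentence exceeds the stated total selection in Scenarios 7, 9 and 11 by about 4 to 14 points (74 − 70 = 4 at the least, 61 − 47 = 14 at the most). It puts 1.7 more patients at 10 mg in Scenario 9 (6.1 − 4.4) and 2.2 more in Scenario 11 (4.9 − 2.7), because it lacks the Case B and C restrictions. The RDS steps match the stated totals closely and Table B's patient numbers approximately. The figures in Section 9.2 therefore describe the stepwise rule and not the bold sentence.

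**What to change.** Reconcile the bold sentence with steps 1–3 so that Section 2.1.2 states one assignment rule. Which rule to use is the sponsor's decision. A reference to the highest RDS alone would not reconcile the text, because Cases B and C restrict the choice regardless of the scores.

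Correct both table references: the opening of Section 2.1.2 for the dose levels, and step 2 for the decision table.

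State that Tables A and B and the figures in Section 9.2 correspond to the stepwise Case A/B/C and RDS rule, and confirm from the simulation settings whether any further exploration step was active. If mean utility is intended, define it (observed or posterior, and its value for an untried dose) and recompute both tables and the Section 9.2 figures.

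The cost is one sentence, two cross-references and a short statement of correspondence. Recomputation is needed only if mean utility is the intended rule.
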